6.3.3.6 Stomatitis and Mucositis

Preventive measures may include a comprehensive oral examination to identify and treat any potential risk for complications before study treatment is initiated. Appropriate correction of local factors should be instituted as indicated, such as modification of ill-fitting dentures and appropriate care of gingivitis. During treatment with cabozantinib, good oral hygiene and standard local treatments such as non-traumatic and non-irritating cleansing, and oral rinses (eg, with a weak solution of salt and baking soda) should be maintained. Lips should be kept moisturized with lip balm. The use of lipstick, lip-gloss, and Vaseline should be avoided.

Local treatment should be instituted at the earliest onset of symptoms. Obtain bacterial/viral culture if oral infection is suspected and treat infection as clinically indicated.

6.3.3.7 Skin and Subcutaneous Tissue Disorders

Wound healing and surgery: Cabozantinib has the potential to cause wound healing complications and wound dehiscence which may even occur long after a wound has been considered healed. Therefore, surgical and traumatic wounds must not only be completely healed prior to starting cabozantinib treatment but must also be monitored for wound dehiscence, wound infection and other signs of impaired wound healing while the subject is being treated with cabozantinib. If dehiscence occurs, cabozantinib treatment should not be restarted until complete healing has taken place.

Treatment with cabozantinib should be stopped at least 28 days prior to scheduled surgery. The decision to resume treatment with cabozantinib after surgery should be based on clinical judgment of adequate wound healing.

Palmar-plantar erythrodysesthesia syndrome (PPES; also known as hand-foot syndrome), skin rash (including blister, erythematous rash, macular rash, skin exfoliation, dermatitis acneiform, and papular rash), pruritus, dry skin, erythema, pigmentary changes, and alopecia have been reported with cabozantinib. All subjects on study should be advised on prophylactic measures including the use of emollients, removal of calluses, avoidance of exposure of hands and feet to hot water leading to vasodilatation, protection of pressure-sensitive areas of hands and feet, and use of cotton gloves and socks to prevent injury and keep the palms and soles dry.

Early manifestations include tingling, numbness, mild hyperkeratosis, and symmetrical red and swollen areas on the palms and soles. The lateral sides of the fingers or periungual zones may also be affected. Adequate interventions are required to prevent worsening of skin symptoms such as blisters, desquamations, ulcerations, or necrosis of affected areas. Analgesics may be required for pain control.

Aggressive management of symptoms is recommended, including early dermatology referral. Treatment recommendations in response to PPES are summarized in Table 6-6.

Table 6-6: Management of Hand-Foot Syndrome (PPES) Associated with Cabozantinib

CTCAE v.4.0 Grade	Action To Be Taken
Grade 1	Cabozantinib treatment may be continued at the current dose if PPES is clinically insignificant and tolerable. Otherwise, cabozantinib should be reduced to the next lower dose level. ^a Start urea 20% cream twice daily AND clobetasol 0.05% cream once daily. Reassess at least weekly; if PPES worsens at any time or does not improve after 2 weeks, proceed to the intervention guidelines for Grade 2.
Grade 2	Cabozantinib treatment may be continued if PPES is tolerated. Cabozantinib should be dose reduced or interrupted if PPES is intolerable. Continue urea 20% cream twice daily AND high potency steroid cream (eg, clobetasol 0.05%) once daily and add analgesics (eg, NSAIDs/gamma-aminobutyric acid agonists) for pain control if needed. Reassess at least weekly; if PPES worsens or affects self-care, proceed to the intervention guidelines for Grade 3.
Grade 3	Interrupt cabozantinib treatment until severity decreases to Grade 1 or 0. Continue treatment of skin reaction with high potency steroid cream (eg, clobetasol 0.05%) twice daily AND analgesics. Resume study drug at a reduced dose if PPES recovers to Grade \leq 1. Discontinue subject from study treatment if PPES does not improve within 6 weeks.

CTCAE, Common Terminology Criteria for Adverse Events; NSAID, non-steroidal anti-inflammatory drug; PPES, palmar plantar erythrodysesthesia syndrome.

^a Permitted dose levels are defined by individual protocols.

6.3.3.8 Osteonecrosis

Osteonecrosis has been reported in subjects treated with cabozantinib. Additional risk factors include use of bisphosphonates and denosumab, chemotherapy and anti-angiogenic drugs, use of corticosteroids, local radiotherapy, and dental or orofacial surgery procedures.

Osteonecrosis of the jaw (ONJ) can manifest as jaw pain, osteomyelitis, osteitis, bone erosion, tooth or periodontal infection, toothache, gingival ulceration, or gingival erosion. Persistent pain or slow healing of the mouth or jaw after dental surgery may also be manifestations of osteonecrosis.

Advise subjects regarding oral hygiene practice and to quickly report symptoms to investigator. Caution should be used in subjects receiving bisphosphonates.

Invasive dental procedures should be avoided. In cases where dental procedures are unavoidable, treatment with cabozantinib should be interrupted for at least 4 weeks prior to the procedure and resumed after complete wound healing has occurred. Bone healing may often require a protracted time.

6.3.3.9 Proteinuria

Proteinuria has been reported with cabozantinib. Proteinuria should be monitored by measuring UPCr. Table 6-7 provides treatment guidelines for proteinuria deemed related to cabozantinib.

Cabozantinib should be discontinued in subjects who develop nephrotic syndrome (proteinuria > 3.5 grams per day in combination with low blood protein levels, high cholesterol levels, high triglyceride levels, and edema).

Table 6-7: Management of Proteinuria Associated with Cabozantinib

Severity of Proteinuria (UPCR)	Management of Proteinuria
≤ 1 mg/mg (≤ 113.1 mg/mmol)	
 No change in cabozantinib treatment or monitoring
> 1 and < 3.5 mg/mg (> 113.1 and < 395.9 mg/mmol)	
 Consider confirming with a 24-h protein assessment within 7 days No change in cabozantinib treatment required if UPCR ≤ 2 mg/mg or urine protein ≤ 2 g/24 h on 24-h urine collection. Dose reduce or interrupt cabozantinib treatment if UPCR > 2 mg/mg on repeat UPCR testing or urine protein > 2 g/24 h on 24-h urine collection. Continue cabozantinib on a reduced dose if UPCR decreases to < 2 mg/mg. Consider interrupting cabozantinib treatment if UPCR remains > 2 mg/mg despite a dose reduction until UPCR decreases to < 2 mg/mg. Restart cabozantinib treatment at a reduced dose after a dose interruption. Repeat UPCR within 7 days and once per week. If UPCR < 1 mg/mg on 2 consecutive readings, UPCR monitoring can revert to protocol-specific times. (Second reading is confirmatory and can be done within 1 week of first reading.) If UPCR remains > 1 mg/mg and < 2 mg/mg for 1 month or is determined to be stable (< 20% change) for 1 month, check urine protein/creatinine per protocol or as clinically indicated.
≥ 3.5 mg/mg (≥ 395.9 mg/mmol)	
 Interrupt cabozantinib treatment pending repeat UPCR within 7 days and/or 24-h urine protein. If ≥ 3.5 mg/mg on repeat UPCR, continue to interrupt cabozantinib treatment and check UPCR every 7 days. If UPCR decreases to < 2 mg/mg, restart cabozantinib treatment at a reduced dose and monitoring of urine protein/creatinine should continue weekly until the UPCR decreases to < 1 mg/mg. If UPCR remains > 1 mg/mg and < 2 mg/mg for 1 month or is determined to be stable (< 20% change) for 1 month, check urine protein/creatinine per protocol or as clinically indicated.
Nephrotic syndrome	
 Discontinue cabozantinib treatment

RCC, renal cell carcinoma; UC, urothelial carcinoma; UPCR, urine protein/creatinine ratio.

6.3.3.10 Nervous System Disorders

Cabozantinib appears to represent minimal risk of adverse neurological effects based on nonclinical Good Laboratory Practice (GLP)-compliant toxicology studies. Dysphonia, dysgeusia, headache, dizziness, confusional state, convulsion, depression, memory impairment, hypoesthesia, peripheral neuropathy, insomnia, ataxia, and encephalopathy have been observed in clinical studies with cabozantinib. The development of any new or progressive, unexplained neurological symptoms should be assessed for underlying causes.

RPLS has been reported. RPLS should be considered in any subject presenting with seizures, headache, visual disturbances, confusion or altered mental function. Cabozantinib treatment should be discontinued in subjects with RPLS.

6.3.3.11 Hepatocellular Toxicity

Elevation of aminotransferases (ALT and AST): Evaluation of subjects with elevated transaminases or bilirubin should be individualized and guided by the presence of specific risk factors such as liver conditions (eg, liver cirrhosis, metastases to the liver, thrombosis of portal or hepatic vein, hepatocellular carcinoma, hepatitis), concomitant hepatotoxic medication, alcohol consumption, and cancer related causes.

Cabozantinib should be interrupted for related CTCAE Grade 3 or higher hepatic injury (transaminase increase to $> 5 \times$ ULN) and when transaminase increases are accompanied by progressive elevations of total bilirubin, and/or elevations of coagulation tests (eg, International Normalized Ratio [INR]). More frequent monitoring of transaminases should be considered and cabozantinib should be interrupted until the etiology of the abnormalities is determined and these abnormalities are corrected or stabilize at clinically acceptable levels. Cabozantinib should be discontinued if hepatic dysfunction is not reversed despite interruption of study treatment. Elevations of aminotransferases when hepatic metastases are present may not require dose modifications if there are no progressive changes in the aminotransferases (less than a doubling) and if there are no progressive elevations in serum bilirubin concentration or coagulation factors. Elevations $>3 \times$ ULN of ALT or AST concurrent with $>2 \times$ ULN total bilirubin without other explanation (such as initial findings of cholestasis and obstructive disease, viral hepatitis, pre-existing or acute liver disease, or another drug capable of causing the observed injury) can indicate drug-induced liver injury (DILI). Study drug should be permanently discontinued in cases determined to be DILI according to Hy's Law review.

6.3.3.12 Infections

Infections are commonly observed in cancer subjects. Predisposing risk factor include a decreased immune status (eg, after myelosuppressive anticancer therapies, splenectomy), destructive growth of the underlying malignancy including bone marrow infiltration with suppression of normal hematopoiesis, as well as the presence of IV devices.

Infections and abscesses should be treated with appropriate local care and systemic therapy. Cabozantinib should be interrupted until adequate healing has taken place.

6.3.3.13 Blood and Lymphatic System Disorders

Hematological toxicities (ie, neutropenia and thrombocytopenia) and associated complications have been observed after administration of cabozantinib and may be managed with dose interruptions and/or dose reductions. Subjects with hematologic toxicities may require additional or more frequent laboratory tests according to institutional guidelines.

Dose reductions or dose interruptions for hematological toxicities are not mandated but can be applied as clinically indicated. Supportive care for thrombocytopenia or anemia, such as

transfusions, may be managed according to institutional guidelines. The use of colony-stimulating growth factors should be considered. Febrile neutropenia or evidence of infection associated with neutropenia must be assessed immediately and treated appropriately and in a timely manner according to institutional guidelines.

6.3.3.14 Fatigue

Common causes of fatigue, such as anemia, deconditioning, emotional distress (depression and/or anxiety), poor nutrition, dehydration, sleep disturbance, and hypothyroidism should be ruled out and treated according to standard of care. Pharmacological management should be considered after disease specific morbidities have been excluded when not prohibited.

6.3.3.15 Weight Loss

Anorexia and weight loss should be managed according to local standard of care including nutritional support. Pharmacologic therapy should be considered for appetite enhancement when not prohibited by a particular protocol.

6.3.3.16 Corrected QT Prolongation

The effect of orally administered cabozantinib 140 mg qd on QTc interval was evaluated in a placebo-controlled study in subjects with MTC. A mean increase in QTcF of 10-15 ms was observed after 4 weeks after initiating cabozantinib treatment. A concentration-QTc relationship could not be definitively established. Changes in cardiac wave form morphology or new rhythms were not observed. No cabozantinib-treated subjects in this study had a QTcF > 500 ms. Review of the larger safety database (~5000 subjects exposed to cabozantinib in clinical trials and in post-marketing experience) confirmed the absence of safety concerns associated with QT prolongation. There were no events of torsades de pointes reported.

Concomitant treatment with strong cytochrome P450 (CYP) 3A4 inhibitors, which may increase cabozantinib plasma concentrations, should be avoided.

If at any time on study there is an increase in QTcF to an absolute value > 500 ms, two additional ECGs must be performed with intervals not less than 3 min apart within 30 min after the initial ECG.

If the average QTcF from the three ECGs is > 500 ms, the following actions must be taken:

- Interrupt cabozantinib treatment
- Hospitalize symptomatic subjects (eg, with palpitations, dizziness, syncope, orthostatic hypotension, a significant ventricular arrhythmia on ECG) for a thorough cardiology evaluation and management
- Consider cardiology consultation for asymptomatic subjects for evaluation and management
- Check electrolytes, especially magnesium, potassium and calcium; correct abnormalities as clinically indicated
- Check concomitant medications for any medication that may have contributed to QT prolongation, and if possible, discontinue these medications (<http://www.qtdrugs.org>)

- Repeat ECG triplicates hourly until the average QTcF is ≤ 500 msec, or otherwise determined by consultation with a cardiologist or appropriate expert.

Subjects with QTc prolongation and symptoms must be monitored closely until the QTc elevation and symptoms have resolved. Cabozantinib treatment may be restarted at a reduced dose level if all of the following conditions are met:

- Symptoms are determined to be unrelated to the QT interval prolongation
- The QTcF value > 500 ms is not confirmed
- Cabozantinib treatment has been interrupted through a minimum of 1 week following the return of the QTcF to ≤ 500 ms.
- QT prolongation can be unequivocally associated with an event other than cabozantinib administration and is treatable/has been resolved

Following reinitiation of study treatment, ECGs must be repeated weekly for 2 weeks, then every 2 weeks for 1 month, then according to the protocol-defined time points.

Cabozantinib treatment must be permanently discontinued if either of the following applies:

- Cardiac evaluation confirms that symptoms are the consequence of QT interval prolongation
- Recurrence of QTcF prolongation after reinitiation of study treatment at a reduced dose

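### In 6.3.3.16, a subject interrupted for a triplicate mean QTcF above 500 ms cannot meet the restart list, if *confirmed* means that triplicate mean

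*Combined protocol and SAP*

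**What the plan says.** All of the operative text is in section 6.3.3.16 of the protocol.

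- **Repeat.** After a QTcF above 500 ms at any time on study, "two additional ECGs must be performed with intervals not less than 3 min apart within 30 min after the initial ECG".
- **Trigger and action.** "If the average QTcF from the three ECGs is > 500 ms, the following actions must be taken"; the first action is "Interrupt cabozantinib treatment".
- **Restart.** "Cabozantinib treatment may be restarted at a reduced dose level if all of the following conditions are met". The four conditions are: first, any symptoms were not due to the QT prolongation; second, "The QTcF value > 500 ms is not confirmed"; third, a waiting period, given as "Cabozantinib treatment has been interrupted through a minimum of 1 week following the return of the QTcF to ≤ 500 ms"; and fourth, another cause, given as "QT prolongation can be unequivocally associated with an event other than cabozantinib administration", with that event treatable or resolved.
- **After restart.** ECGs are repeated on a set schedule: weekly for 2 weeks, then two-weekly for 1 month, then at the protocol's usual times.
- **Permanent discontinuation.** Either of two findings requires it: symptoms shown by cardiac evaluation to result from the prolongation, or "Recurrence of QTcF prolongation after reinitiation of study treatment at a reduced dose".

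The note to exclusion criterion 9 (section 4.2) uses the same method at entry: a single value above 500 ms is followed by two more ECGs, and the mean of the three decides.

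**The concern.** The interruption trigger and the second restart condition appear to describe opposite findings. The section interrupts treatment because the repeat ECGs bore out the high value, and then makes restart depend on the high value not having been borne out. Because the restart conditions are cumulative, one condition that cannot be met closes the whole list.

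This is a cardiac safety rule, and it should be possible to apply it on the day it is needed. If it cannot be applied as written, an investigator with a resolved, confirmed value has two courses: to restart against a listed condition, or to stop for good without a sentence in the section that calls for it. The protocol should not leave that choice to the reader of a single bullet.

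**Working it through.** The plan gives no figure to reproduce here and no arithmetic applies. The check sets the sentences of 6.3.3.16 side by side.

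**Definitions.** Let C stand for a mean QTcF above 500 ms over the three ECGs. Let R1 to R4 be the four restart conditions in the order listed under what the plan says.

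**Step 1: what *confirmed* means.** The documents do not define the word. The only procedure they give for checking a high QTcF is to repeat the ECG and average three, in 6.3.3.16 and again in exclusion criterion 9. In that sense, *confirmed* is C and R2 is not-C.

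**Step 2: combine trigger and restart.**

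- Interruption ordered by 6.3.3.16 requires C.
- Restart requires R1 and not-C and R3 and R4.
- Interrupted under 6.3.3.16 and eligible to restart therefore requires C and not-C, which is impossible whatever R1, R3 and R4 are.

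| Case | Interruption ordered by 6.3.3.16? | R2 | Restart list |
|---|---|---|---|
| C true | Yes | Fails | Cannot be met |
| C false, treatment continues | No | Holds | No restart question arises |
| C false, treatment held at investigator discretion under 6.3 | No | Holds | Can be met if R1, R3 and R4 also hold |

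**Step 3: does the section otherwise expect restart?** R3 speaks of a QTcF that has come back to 500 ms or below, and R4 of a prolongation that has a cause. Both take the prolongation as real. The ECG schedule after restart and the rule on recurrence are written for a subject who had a prolongation, restarted and may have another. On the reading in step 1, no subject in the first row of the table can reach those provisions.

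**Step 4: where does the first-row subject go instead?** Take a subject with C true, a value since returned to 500 ms or below, and no symptoms caused by the prolongation.

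- Restart: barred by R2.
- Permanent discontinuation under 6.3.3.16: the symptom limb does not apply, and the recurrence limb needs a prior restart.
- The discontinuation list in 6.3.3: QTc prolongation is not on it.
- The six-week limit in 6.3: it covers interruptions for related AEs. If the prolongation is traced to another event, as R4 requires, 6.3 lets the interruption run longer at the investigator's discretion.

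The general power in section 3 to withdraw a subject for an AE remains available, but it is not a rule for this case. As written, the subject has neither a route back nor a stated end to the interruption.

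**The case against.** **The word is undefined and could mean something else.** The condition is in the present tense, and the section provides for later triplicates and for cardiology input. A high value no longer found at that later evaluation might count as not confirmed, and the list could then be met. This stands as a limit: the conclusion depends on the sense of *confirmed*. However, the text does not state the later sense, and it would largely duplicate the condition on return to 500 ms or below. If it is intended, it has to be written.

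**6.3.3.16 is not the only route to interruption.** Section 6.3 lets the investigator interrupt at any time for related AEs. A subject held after a single high reading with a mean at or below 500 ms would meet R2, and could meet R4 if another cause was then established. This stands. A reader might infer that nobody in the trial can ever meet the list; the documents support that only for interruptions ordered by 6.3.3.16.

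**R2 and R3 can hold together.** The same subject could meet both. A reader might infer that these two conditions exclude each other, and they do not. The conflict is between R2 and the interruption trigger.

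**Restart is permitted, not required.** A site that finds R2 unmet and does not restart breaches nothing, and the rules that follow apply only if a restart happens. A reader might infer that sites must break one sentence to obey another. The text does not support this. What it contains is a permission that the subjects it addresses cannot use.

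**The general restart rule in 6.3.1 might serve.** It allows treatment to resume on recovery. But 6.3.3.16 sets its own cumulative list for QTc prolongation, and nothing says that the general rule displaces it.

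**The event should be rare.** The protocol reports no QTcF above 500 ms in the placebo-controlled study at 140 mg and no QT safety concern in about 5000 exposed subjects. The starting dose here is 60 mg, entry excludes QTcF above 500 ms, and after Day 1 the only scheduled on-treatment ECG is at week 6. This stands in full and limits the expected impact. It does not make the rule workable.

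**Consequences for the endpoint.** A reader might infer that like patients will be handled differently, or that week-12 responses will be lost. Nothing in the documents shows either. Table 5-1 schedules a tumor assessment after the last dose, and a footnote allows it within 28 days, so early stopping does not by itself remove the scan.

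**Conclusion.** Wrong as written, with low expected impact.

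If *confirmed* has its only documented sense, the mean of the three ECGs, then no subject whose interruption was ordered by 6.3.3.16 can satisfy the restart list. The same section provides for restart and for recurrence after it. The subject with a confirmed, resolved value and no symptoms caused by it falls between the restart list and the permanent-discontinuation list.

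The conclusion rests on two things: that sense of *confirmed*, and the cumulative wording of the restart list. It does not extend to discretionary holds under 6.3.

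With 17 patients planned and no QTcF above 500 ms in the study the protocol cites, the rule may never be called on. The Simon two-stage figures in section 9 (11 then 6 patients, 3 or more responses of 17 to reject, response rates of 5% and 24%) do not depend on this rule and do not change.

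**What to change.** Reconcile the three parts of 6.3.3.16 with one another: the interruption trigger, the restart list and the permanent-discontinuation list.

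- Define *confirmed*: which ECGs, taken when, and read by whom.
- State which restart conditions are cumulative and which are alternatives, and check that a subject interrupted under the section can satisfy the list if restart is meant to be possible.
- State what happens to a subject with a confirmed value that has resolved and who has no symptoms caused by the prolongation.
- If restart after a confirmed value is not intended, say so and bring the post-restart and recurrence provisions into line.

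Which clinical rule applies is for the sponsor and investigator to decide; the point here is only that the sentences must agree. The cost is rewording one subsection in an amendment. Sample size, endpoints and analysis are unaffected.
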